6.6.2. Laboratory Data

Laboratory data will be listed and summarized in accordance with the CaPS. Summaries of participants meeting pre-specified monitoring and discontinuation criteria will be created using methods for categorical data (see Section 5.2.4).

Laboratory data on or after day of Tdap vaccines will also be reported for participants in the sub-study.

6.6.3. Vital Signs, including Height and Weight

Vital signs will be summarized at Baseline and at Weeks 2, 4, 8 and 12. Height will be reported at the Screening Visit and Week 12. Weight will be summarized at baseline and Week 12.

6.6.4. Electrocardiograms

ECG parameters, if applicable, will be summarized at by visits.

6.6.5. Physical Examination

Physical examinations will be summarized at baseline and all-available post-baseline visits.

7. INTERIM ANALYSES

This study uses an External Data Monitoring Committee (E-DMC). The E-DMC will be responsible for ongoing monitoring of the efficacy and safety of participants in the study according to the charter. The recommendations made by the E-DMC to alter the conduct of the study will be forwarded to Pfizer for final decision. Pfizer will forward such decisions, which may include summaries of aggregate analyses of endpoint events and of safety data that are not endpoints, to regulatory authorities, as appropriate. Composition of the E-DMC and processes under which the E-DMC operates will be documented in the E-DMC charter.

9. APPENDICES

Appendix 1. Summary of Efficacy Analyses

Efficacy Endpoints	Population	Analysis Method	Missing Data Imputation	Primary Analysis for Co-primary Endpoints
Week 12 IGA Response	FAS	CMH	NR	Yes
Week 12 IGA Response	PPAS	CMH	NR	No
Week 12 IGA Response	FAS	CMH	TP	No
Week 12 EASI-75 Response	FAS	CMH	NR	Yes
Week 12 EASI-75 Response	PPAS	CMH	NR	No
Week 12 EASI-75 Response	FAS	CMH	TP	No
Weeks 2, 4, and 12 NRS4 for severity Response	FAS	CMH	NR	
Weeks 1-12 CFBL in PSAAD	FAS	MMRM	OD	
Days 2-15 and Week 8 NRS4 for Severity Response	FAS	CMH	NR	
Time to NRS4 for severity	FAS	Time to Event		
Weeks 2, 4 and 8 IGA, EASI-75 Response	FAS	CMH	NR	
Weeks 2, 4, 8 and 12 EASI-50, EASI-90, EASI-100 Response	FAS	CMH	NR	
Weeks 2, 4, 8 and 12 Percent CFBL in Total EASI Score	FAS	MMRM	OD	
Days 2-15, Weeks 4, 8 and 12 Percent CFBL in NRS for severity	FAS	MMRM	OD	
Weeks 2, 4, 8 and 12 CFBL and Percent CFBL in %BSA	FAS	MMRM	OD	
Weeks 2, 4, 8 and 12 SCORAD50, SCORAD75 Response	FAS	CMH	NR	

090177e19618b8f5\Approved\Approved On: 25-Jan-2021 08:47 (GMT)

Weeks 2, 4, 8 and 12 CFBL and Percent CFBL in SCORAD Total Score, SCORAD (VAS) for sleep loss	FAS	MMRM	OD	
CFBL=Change from baseline; CMH=Cochran-Mantel-Haenszel; ANCOVA=Analysis of Covariance; MMRM=Mixed-effect Model Repeated Measures; NR=Non-Responder; OD=Observed Data; TP=Tipping Point				

090177e19618b8f5\Approved\Approved On: 25-Jan-2021 08:47 (GMT)

Appendix 2. Definition and Use of Visit Windows in Reporting

Visit windows will be used for efficacy variables, and for any safety data that display or summarize by study visit. For other endpoints (eg, ECG, vital signs), visit windows will be applied for summary statistics by study visits if required.

Visit Label	Target Day	Definition [Day window]
Baseline	Day 1 (Day of first dose)	Last observation prior to and including day of first dose
Week 2	15	Days 2 to 22
Week 4	29	Days 23 to 43
Week 8	57	Days 44 to 71
Week 12	85	Days 72 to 99
Follow Up/End of Study		
Week 16	113	Days 100 to -

For the lab values, if the calculated study day for the labelled baseline visit is not study Day 1 but falls within 28 days before the start of the study dosing, then that data should be used for the baseline instead of leaving baseline missing.

For the other values, if the calculated study day for the labelled baseline visit is not study Day 1, but falls before the start of the study dosing, then that data should be used for the baseline instead of leaving baseline missing.

If two or more visits fall into the same window, keep the one closest to the Target Day. If two visits are equaled distant from the Target Day in absolute value, the later visit should be used.

Observations on the actual day will be used to analyze Days 2-15 Pruritus NRS. Weeks 2, 4, 8 and 12 Pruritus NRS will be based on the windowing method.

Safety analysis will follow CaPS.

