1.3. Schedule of Activities (SoA)

Visit Identifier	Screening		Intervention Period								Follow-up		Notes
	Day -28	Visit 1	Day 1	Day 8	Day 15	Day 29	Day 43	Day 57	Day 85	Day 113	Week 16 (EOS)		
			Week 0 Baseline (by Phone)	Week 1 (by Phone)	Week 2	Week 4	Week 6 (by Phone)	Week 8	Week 12 (EOT/ET)				
	Visit 1	Visit 2	Visit 3	Visit 4	Visit 5	Visit 6	Visit 7	Visit 8	Visit 9			Visit 9 is 4 weeks after last dose in case of early study termination	
Visit Window (days)	None	None	±1	±1	±2	±3	±3	±3	±3				
Enrollment Procedures													
Informed consent/assent	X												
Register subject using IRT	X												
Inclusion and exclusion criteria	X		X										
Demographics, Medical History, Tobacco and Alcohol History, AD Disease History and prior AD treatments	X												
Review Prior/Concomitant Medications & Treatments	X	X	X	X	X	X	X	X	X	X	X		
Dispense eDiary and instruct participants on use	X												

Visit Identifier	Screening	Intervention Period										Follow-up	Notes	
		Day -28	Day 1	Day 8	Day 15	Day 29	Day 43	Day 57	Day 85	Day 113	Week 16 (EOS)			
Instruct participants on washout of pre-baseline medications (if applicable)	X													See inclusion criteria #3 (Section 5.1) and exclusion criteria #16 (Section 5.2)
Train participants on use of background topical therapy for AD and daily recording in eDiary	X	X	X	X	X	X	X	X	X	X	X			See Section 6.5.1
Provide Patient Emergency Contact Card	X													
Medical Procedures														
Complete physical examination	X	X								X				See Section 8.2.1
Targeted Physical Exam				X	X					X		X		
Vital Signs (pulse rate, blood pressure, temperature)	X	X		X	X					X		X		See Section 8.2.2 Temperature collection applies to Germany and UK only. Temperature data will be recorded in source documents only.
Weight	X	X										X		See Section 8.2.1
Height	X											X		See Section 8.2.1

Visit Identifier	Screening	Intervention Period								Follow-up	Notes
		Day -28	Day 1	Day 8	Day 15	Day 29	Day 43	Day 57	Day 85		
	X	Week 0 Baseline (by Phone)	Week 1 (by Phone)	Week 2	Week 4	Week 6 (by Phone)	Week 8	Week 12 (EOT/ET)	Week 16 (EOS)		Visit 9 is 4 weeks after last dose in case of early study termination
Chest Imaging / X-Ray	X										Recommended but not mandatory For Germany only: If chest imaging is considered medically necessary, MRI may be performed.
ECG (12-lead)	X	X		X	X		X	X	X		Central reading
Laboratory Procedures											

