Serum chemistry and hematology (including coagulation panel)	X	X		X	X		X	X	X		See Appendix 2 See Section 8.2.8 for guidance on abnormal lab results
Lipid Panel		X			X			X	X		After 8-hour fast, when possible
CCI											
CCI											
Urinalysis	X	X		X	X		X	X	X		See Appendix 2

Visit Identifier	Screening	Intervention Period							Follow-up	Notes			
		Day -28	Day 1	Day 8	Day 15	Day 29	Day 43	Day 57			Day 85	Day 113	
Serum pregnancy test	X												Visit 9 is 4 weeks after last dose in case of early study termination
Urine Pregnancy Test (conducted at study site)		X			X	X		X		X			Required for all WOCBP
Blood Samples Collection for Viral Studies		X			X	X			X				Only analyzed on suspected viral infection/reactivation.
HIV Testing	X												
Hepatitis B (HBsAg, HBsAb and HBcAb) and Hepatitis C (HCV Ab, HCV RNA)	X												See Section 8.2.8.1
HBV DNA	X								X				Only for China, Taiwan, Japan and countries where HBV DNA testing is required (see Section 8.2.8.1 for country-specific guidance for assessment)
Varicella Zoster Virus IgG Ab	X												See Section 8.2.8.2
Tuberculosis Test	X												See Section 5.2 and Section 8.2.4

Visit Identifier	Screening	Intervention Period										Follow-up	Notes	
		Day -28	Day 1	Day 8	Day 15	Day 29	Day 43	Day 57	Day 85	Day 113	Week 16 (EOS)			
		Week 0 Baseline	Week 1 (by Phone)	Week 2	Week 4 (by Phone)	Week 6	Week 8	Week 12 (EOT/ET)						Visit 9 is 4 weeks after last dose in case of early study termination
Pharmacokinetic														
Pharmacokinetic Blood Sampling (Pre-dose)							X							22 hours after last dose (±30 min)
Pharmacokinetic Blood Sampling (Post-dose)								X						2 hours post-dose (±30 min)
Study Treatment														
Randomization		X												
Drug dispensing		X			X		X							
Drug accountability				X	X		X							
Study intervention treatment		X	-----X											
Review eDiary to assess treatment compliance			X	X	X	X	X	X	X	X	X	X	X	
Assess eligibility for B7451015												X		
Application of non-medicated topical therapy at home	X	-----X											At least 7 days before Day 1 (see Section 6.5.1)	

Visit Identifier	Screening	Intervention Period							Follow-up	Notes
		Day 1	Day 8	Day 15	Day 29	Day 43	Day 57	Day 85		
	Day -28	Week 0 Baseline (by Phone)	Week 1 (by Phone)	Week 2	Week 4	Week 6 (by Phone)	Week 8	Week 12 (EOT/ET)	Day 113 Week 16 (EOS)	Visit 9 is 4 weeks after last dose in case of early study termination

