4.3. Justification for Dose

Dose selection for Phase 3 was based on efficacy and safety of PF-04965842 from a dose-ranging Phase 2b study, B7451006 that evaluated a 20-fold dose range (10 mg to 200 mg QD) in adults with moderate-to-severe AD. The 200 mg QD dose is expected to provide efficacy similar to that of currently approved systemic treatments in moderate-to-severe AD, and was therefore selected as the high dose for evaluation in Phase 3 studies. An additional dose of 100 mg QD was also selected for evaluation in Phase 3, since this dose is expected to provide clinically efficacy in IGA response, while differentiating from the higher dose in terms of expected efficacy and systemic exposure. This will inform the selection of the dose with the most optimal benefit-risk. Both 100 mg and 200 mg QD doses demonstrated acceptable safety and tolerability in the Phase 2 study. There was no evidence of dose-dependent changes in safety endpoints such as serious infections or adverse events. Dose-response was evident only for changes from baseline in platelet counts. Mean platelet count decreases from baseline were observed with a nadir at Week 4. At Week 4 the mean platelet count and the 90% confidence interval (CI) were within the normal reference range for the 100 mg dose and 200 mg dose. The mean platelet counts increased towards baseline after Week 4. One (1) PF-04965842 treated subject with an adverse event (AE) of thrombocytopenia, had a value less than 0.5 x lower limit of normal. There were no reported adverse clinical effects potentially associated with reduced platelet counts, such as bleeding events, observed in the Phase 2 study. Further details are available in the IB.

The emerging efficacy and safety data in this study will be monitored periodically by E-DMC to ensure acceptable benefit-risk for this patient population.

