 - Two sequential AST or ALT elevations >3 times the upper limit of normal with an abnormal international normalized ratio (INR).
 - Two sequential AST or ALT elevations >3 times the upper limit of normal accompanied by symptoms consistent with hepatic injury.
 - Two sequential AST or ALT elevations >5 times the upper limit of normal, regardless of total bilirubin or accompanying symptoms.

NOTE: Any of the above findings should prompt review of “The Potential Cases of Drug-Induced Liver Injury,” Appendix 6 for which additional investigations must be conducted.

- Two sequential increases in serum creatinine that are $>50\%$ over the average of screening and baseline values AND an absolute increase in serum creatinine $\geq 0.5 \text{ mg/dL}$. At the time of study completion or discontinuation, if a subject should exhibit elevations in serum creatinine $\geq 33\%$ above the average of screening and baseline values, they will be re-tested every 1 to 2 weeks until the serum creatinine elevation is fully reversed to within 10% of the average of screening and baseline values or has stabilized.

Having met Discontinuation Criteria, the participant must be permanently withdrawn from treatment, have their end of treatment visit, and will then enter the 4-week follow-up period.

Additional individual participant safety monitoring, including laboratory testing or unscheduled study visits, in addition to these guidelines is at the discretion of the investigator and dependent on any perceived safety concerns. Unscheduled laboratory testing through the central laboratory may be obtained at any time during the study to assess such concerns.

If a participant has a clinically significant, treatment emergent, abnormality at the time of withdrawal from the study, the Pfizer clinician (or designee) should be notified and every effort should be made to arrange follow-up evaluations at appropriate intervals to document the course of the abnormality. All abnormal laboratory events of clinical significance should be followed until the laboratory values have returned to normal or baseline levels or are deemed clinically stable. Follow-up for abnormal laboratory findings and adverse events by the investigator is required until the event or its sequelae resolve or stabilize at a level acceptable to the investigator, and Pfizer concurs with that assessment.

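### SAP Appendix 2 has no last-dose condition, so for nearly all participants who stop before Day 72 the off-drug Visit 9 falls in the Week 4, 8 or 12 window and its scores enter the hypothetical-estimand MMRM

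*SAP*

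**What the plan says.** **Windows.** SAP Appendix 2 states: "Visit windows will be used for efficacy variables, and for any safety data that display or summarize by study visit". The windows are Days 2-22 (Week 2), 23-43 (Week 4), 44-71 (Week 8), 72-99 (Week 12) and Day 100 onward (Week 16, under the Follow Up/End of Study heading). For competing visits: "If two or more visits fall into the same window, keep the one closest to the Target Day"; a tie goes to the later visit. No rule refers to the last dose. The appendix closes with "Safety analysis will follow CaPS".

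**Timing of the follow-up visit.** The Schedule of Activities (Protocol 1.3) notes: "Visit 9 is 4 weeks after last dose in case of early study termination". Its visit-window row ends at ±3 days. Under Protocol Appendix 5, participants who meet discontinuation criteria "have their end of treatment visit, and will then enter the 4-week follow-up period".

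**Continuous endpoints.** SAP 2.1.2.1 defines a hypothetical estimand, the effect had everyone stayed on assigned treatment. Its intercurrent-event entry nevertheless keeps everything collected, and SAP 6.2.3.3 repeats this for the MMRM of BSA, EASI, SCORAD and Peak Pruritus NRS. Protocol 9.1.1 defines the same estimand but censors data after discontinuation of treatment.

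**The concern.** The windows suit a completer: last visit on Day 85, follow-up on Day 113. An early stopper's follow-up visit moves with the last dose, while the row meant to receive it stays at Day 100 and later. A visit about four weeks off drug is therefore reported under a treatment-period week.

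Two kinds of output are exposed. By-visit MMRM estimates would mix on-drug and off-drug scores while claiming to estimate the effect under continued treatment. By-visit safety summaries would mix them too, and an arm with more early stops would contribute more off-drug values to its later weeks.

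**Working it through.** **Inputs**
- Target days 15, 29, 57, 85, 113 and window limits: SAP Appendix 2.
- Visit 9 on day L + 28 + w, where L is the day of last dose and w runs from -3 to +3: Protocol 1.3.
- Longest multiple-dose mean half-life, 5.0 hours: Protocol 2.2.3.
- Delay e from last dose to the end-of-treatment visit: not in the documents. I take e = 0 to 14 days as an assumption.

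**Step 1. Reproduce the windows.** The upper limits are midpoints of adjacent target days: (15+29)/2 = 22, (29+57)/2 = 43, (57+85)/2 = 71, (85+113)/2 = 99. The Week 16 target is 85 + 28 = 113.

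**Step 2. Nominal timing (w = 0).**

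| Last dose, L | Visit 9, L + 28 | Window |
|---|---|---|
| 1-15 | 29-43 | Week 4 |
| 16-43 | 44-71 | Week 8 |
| 44-71 | 72-99 | Week 12 |
| 72 or later | 100 or later | Week 16 |

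All 71 last-dose days before Day 72 land outside the follow-up row. A participant whose last dose is on Day 29 has Visit 9 on Day 57, exactly the Week 8 target day.

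**Step 3. With the ±3 days.** Visit 9 is certain to miss the follow-up row only if L + 31 ≤ 99, so L ≤ 68. For L = 69, 70 and 71, one, two and three of the seven permitted days reach Day 100 or later. Of 71 × 7 = 497 combinations, 497 - 6 = 491 (98.8%) fall in Week 4, 8 or 12. Conversely, L = 72-74 with an early visit can still fall in Week 12 (74 + 25 = 99). These are counts of combinations, not probabilities.

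**Step 4. Competing visits, at nominal timing.** If the end-of-treatment visit is on the last-dose day, it is 28 days before Visit 9. No Week 4-12 window is longer than 28 days, so the two cannot compete. With a delay they can:

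| e (days) | Last-dose days (of 71) where another visit displaces Visit 9 |
|---|---|
| 0 | 0 |
| 1 | 2 |
| 3 | 4 |
| 7 | 8 |
| 14 | 21 |

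Unscheduled visits are not modelled and could displace more.

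**Step 5. Is Visit 9 off drug?** 28 × 24 / 5.0 = 134 half-lives, so drug is absent. This says nothing about whether a laboratory value or skin score has returned to baseline.

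**Step 6. Effect on a by-visit mean.** If a share f of an arm's values at a visit comes from Visit 9, the raw mean is (1 - f) × on-drug mean + f × off-drug mean. The documents do not give f. Assuming f = 3% to 10% (about 2 to 8 of 75), and assuming off-drug scores match placebo and these participants would otherwise have shown the average effect, a true difference D becomes 0.97 D to 0.90 D. The MMRM is not a raw mean, so this shows only the order of size.

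**The case against.** **CaPS may already handle safety data.** Appendix 2 and SAP 6.6.2 both defer to it, and it cannot be checked here. This stands, so the safety part is conditional. But SAP 3.5.1 writes out the last-dose-plus-28-days rule for adverse events, and nothing similar is written for by-visit laboratory data.

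**Using all data is the SAP's stated choice, and the SAP may modify the protocol.** That would settle the conflict between the documents, but not the one inside SAP 2.1.2.1, where the estimand assumes continued treatment. If Protocol 9.1.1 governs instead, the MMRM problem disappears, but the SAP does not say so.

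**The mapping is not universal.** A reader might infer that every early stopper is affected. Non-attenders, late visits after a last dose on Days 69-71, and closer end-of-treatment visits are exceptions.

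**Recovered platelets.** A reader might infer that recovered counts mask a drug effect, since Protocol 4.3 says "Mean platelet count decreases from baseline were observed with a nadir at Week 4". The documents give no recovery time after stopping, no discontinuation rates by arm in this trial and no on-drug versus off-drug difference. The same section reports mean counts rising toward baseline after Week 4, so the gap may be smaller later. SAP 6.6.2 also counts participants who meet monitoring and discontinuation criteria, so severe cases are not hidden.

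**Lipids.** They are not scheduled at Week 8, so there is no planned Week 8 on-drug lipid summary to distort.

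**Conclusion.** The point holds for nearly all participants who stop before Day 72 and attend Visit 9, unless another visit is closer to the target day. As written, the by-visit MMRM analyses admit off-drug scores that contradict their own estimand and the protocol's censoring rule. The number affected depends on early stopping, which Protocol 7.2 expects to be uncommon for withdrawal from the study. At the assumed 3% to 10% share, the effect on a treatment difference is modest. Its direction is not assured, because scores after stopping may also reflect other treatment.

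By-visit laboratory, vital sign and ECG summaries are exposed under the Appendix 2 text unless CaPS says otherwise. The size of any laboratory bias is unknown.

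A reader might also infer that the co-primary results are distorted. This point does not support that: SAP 6.1.1.1 and Protocol 9.1.1 impose non-response after dropout or treatment discontinuation. The different trigger in SAP 5.3.1 is a separate matter. The MMRM endpoints named here are outside the multiplicity procedure (SAP 5.1), and the key secondary PSAAD uses weekly diary averages.

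**What to change.** In SAP Appendix 2:
- Make Visit 9, and any assessment beyond a stated lag after last dose, ineligible for the Week 2-12 windows.
- Keep the end-of-treatment visit in its study-day window, identified by visit label, because Protocol Appendix 5 sets no deadline for it.
- Put later assessments in a post-treatment/follow-up row, labelled as four weeks after last dose only when the assessment is Visit 9.

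Apply this to the hypothetical-estimand MMRM analyses, and reconcile SAP 2.1.2.1 and 6.2.3.3 with Protocol 9.1.1. Apply it also to by-visit laboratory, vital sign and ECG summaries, stating whether it matches or overrides CaPS. Leave the treatment-policy analysis unchanged, since it is meant to use off-drug data.

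The cost is SAP wording and one derivation flag, with no new data. The downside is slightly fewer values at Weeks 4-12. At nominal timing, the last-dose days before Day 72 that send Visit 9 to a Week 4-12 window fall from 71 of 71 to 0 of 71.

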8.2.8. Clinical Safety Laboratory Assessments

- See Appendix 2 for the list of clinical laboratory tests to be performed and the Schedule of activities for the timing and frequency.
- When possible, participants should abstain from all food and drink (except water and non-study medications) for an 8-hour overnight fast prior to labs that include the lipid profile panel on Day 1, Week 4, Week 12, and EOS. All other labs do not require fasting.
- Sample collection, labeling, storage, and shipping information can be found in the laboratory manual.
- The investigator must review the laboratory report, document this review, and record any clinically relevant changes occurring during the study in the AE section of the CRF. The laboratory reports must be filed with the source documents. Clinically significant abnormal laboratory findings are those which are not associated with the

underlying disease, unless judged by the investigator to be more severe than expected for the participant's condition.

- All laboratory tests with values considered clinically significantly abnormal during participation in the study or within 28 days after the last dose of study intervention should be repeated until the values return to normal or baseline or are no longer considered clinically significant by the investigator or Pfizer clinician.
 - If such values do not return to normal/baseline within a period of time judged reasonable by the investigator, the etiology should be identified and the sponsor notified.
 - All protocol-required laboratory assessments, as defined in Appendix 2, must be conducted in accordance with the laboratory manual and the Schedule of activities.
 - If laboratory values from non-protocol specified laboratory assessments performed at the institution's local laboratory require a change in participant management or are considered clinically significant by the investigator (eg, SAE or AE or dose modification), then the results must be recorded in the CRF.

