10.5. Appendix 5: Monitoring and Discontinuation Criteria

Monitoring Criteria

The following laboratory abnormalities require prompt retesting:

- Neutrophil counts <1000 neutrophils/mm³; confirmed promptly by repeat testing, ideally within 3-5 days;
- Platelet counts $<75,000$ platelets/mm³; confirmed promptly by repeat testing, ideally within 3-5 days;
- Any single hemoglobin value <9.0 g/dL or one that drops ≥ 2 g/dL below baseline; confirmed promptly by repeat testing, ideally within 3-5 days;
- Any single AST and/or ALT elevation >3 times the upper limit of normal regardless of accompanying symptoms or the total bilirubin should prompt repeat testing. This should also prompt review of Appendix 6 (Liver Safety); additional investigations must be conducted.

Temporary Interruption to Dosing

Temporary interruption to dosing is not allowed in this study, except when indicated for participant safety. Sponsor clinician must be informed when temporary interruption occurs and the duration of temporary interruption must not exceed 14 days.

Discontinuation Criteria

Participants must be permanently discontinued from treatment if they meet any of the following criteria at any point in the study:

- Marked prolongation of the QTcF interval to >500 ms or >60 ms change from screening ECG.
- Serious infection (see definition for Serious Adverse Events in Section 10.3.2).
- Any bleeding event thought to be associated with a platelet count reduction per the judgement of the investigator (or, if necessary/desired, following discussion with sponsor).
- Adverse event, per judgment of the investigator, requiring discontinuation from treatment (or, if necessary/desired, following discussion with sponsor).
- Confirmed pregnancy (as described in Section 8.2.10)

NOTE: any initial lab value below must be retested within 48 hours.

- Two sequential platelet counts $<50,000/\text{mm}^3$. If the subject has a platelet count $<25,000/\text{mm}^3$, study intervention should be temporarily withheld pending the confirmatory retest.
- Two sequential neutrophil counts $<500/\text{mm}^3$.
- Two sequential lymphocyte counts $<500/\text{mm}^3$.
- Two sequential hemoglobin assessments $<8.0 \text{ g/dL}$ and / or a decrease of $> 30\%$ from baseline value.
- Any of the following:
 - Two sequential AST or ALT elevations >3 times the upper limit of normal with at least one total bilirubin value >2 times the upper limit of normal.

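### Under the SAP's visit-window rule, a confirmatory laboratory retest can displace the scheduled abnormal value that triggered it in by-visit tables, if the visit was early and the retest prompt

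*SAP*

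**What the plan says.** SAP Appendix 2 sets the scope of the windows: "Visit windows will be used for efficacy variables, and for any safety data that display or summarize by study visit". The laboratory baseline clause in the same appendix shows that laboratory data are included. The windows are Days 2-22 (Week 2, target Day 15), 23-43 (Week 4, target 29), 44-71 (Week 8, target 57) and 72-99 (Week 12, target 85).

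Where a window holds more than one visit, the rule is: "If two or more visits fall into the same window, keep the one closest to the Target Day". The tie-break is: "If two visits are equaled distant from the Target Day in absolute value, the later visit should be used". Nothing gives a scheduled sample precedence or excludes an unscheduled repeat. The appendix closes by saying that safety analysis follows CaPS, and SAP Section 6.6.2 says the same of laboratory data.

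The protocol creates the competing records. In Appendix 5, neutrophil, platelet and hemoglobin values past the monitoring limits are to be "confirmed promptly by repeat testing, ideally within 3-5 days". For the discontinuation-level laboratory criteria: "NOTE: any initial lab value below must be retested within 48 hours". Protocol Section 8.2.8 adds that clinically significant abnormal results "should be repeated until the values return to normal or baseline or are no longer considered clinically significant".

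**The concern.** A rule that picks the record nearest a target day is neutral when extra records arise for reasons unrelated to the value. Here they do not: a retest exists mainly because the scheduled value was abnormal. When the rule prefers the retest, it drops the triggering value and keeps one that is likely to be less extreme. Regression to the mean works in that direction, and so does repeating a test until it normalises. For very low platelet counts, Appendix 5 has study drug withheld pending the retest, so the value kept could have been taken off drug.

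By-visit summaries of laboratory values and change from baseline are where a dose-related platelet decrease would be read against placebo. Protocol Section 4.3 reports such a decrease in Phase 2, with its nadir at Week 4. If abnormal values are more frequent on active drug, selective replacement would tend to narrow the contrast. Whether a given triggering value appears would then depend partly on the appointment date.

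**Working it through.** The documents state no figure on this point, so the rule was applied directly.

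**Inputs**
- Permitted visit deviation (Protocol Section 1.3): Day 15 ±1, Day 29 ±2, Days 57 and 85 ±3.
- Targets, windows and tie-break: SAP Appendix 2.
- Retest lag r: 1-2 days for the 48-hour requirement, if timed from the draw; 3-5 days for the monitoring limits (Protocol Appendix 5).

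**Do both records share a window?** The latest retest in each case is 16+5 = Day 21 (limit 22), 31+5 = 36 (limit 43), 60+5 = 65 (limit 71) and 88+5 = 93 (limit 99). Every 1-5 day retest after an in-window visit therefore competes with its scheduled sample.

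**Condition for replacement.** Let the scheduled visit be e days before target. The scheduled record is at distance e and the retest at |r − e|. The retest is kept if |r − e| ≤ e, equality being included because ties go to the later record. This reduces to r ≤ 2e. If the visit is on the target day or x days after it, the retest is at x + r, which exceeds x, so the scheduled value is always kept.

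**Examples**
- Day 54, retest Day 57: distances 3 and 0, retest kept.
- Day 27, retest Day 31: distances 2 and 2, retest kept by the tie-break.
- Day 56, retest Day 59: distances 1 and 2, scheduled value kept.

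**Share of permitted visit days on which the retest replaces the scheduled value**

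| Lag r | Days early needed | Week 2 (3 days) | Week 4 (5 days) | Weeks 8 and 12 (7 days each) |
|---|---|---|---|---|
| 1-2 | at least 1 | 1/3 = 33% | 2/5 = 40% | 3/7 = 43% |
| 3-4 | at least 2 | 0 | 1/5 = 20% | 2/7 = 29% |
| 5 | at least 3 | 0 | 0 | 1/7 = 14% |

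These are expected shares only if each permitted visit day is equally likely.

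**Early visits alone.** There are 1+2+3+3 = 9 early visit days over the four visits. At lags 1-2 the retest is kept in 18 of 9×2 = 18 combinations. At lags 3-5 it is kept in 12 of 9×3 = 27: two at Week 4, five at Week 8 and five at Week 12. The total is 30 of 45. If a scheduled record took precedence whenever one exists, it would be 0 of 45. These count day combinations, not expected frequencies.

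**Effect per replacement.** With 75 per arm, one participant is 1/75 = 1.3 percentage points of an abnormal category at that visit. This is an upper bound, reached only if the retest is normal.

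**The case against.** **The sponsor standard may already settle it.** CaPS is named as governing safety analysis in the same appendix and again in SAP Section 6.6.2, and it may restrict by-visit tables to scheduled records. This stands as a limit on what can be concluded. It does not remove the point: the written rule covers by-visit safety data, and if CaPS differs, the two conflict.

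**The rule speaks of visits.** Protocol Appendix 5 mentions extra laboratory testing and unscheduled visits separately, so a laboratory-only retest might not count as a visit. The term is undefined, and SAP Section 5.3.1 uses these windows to map all observed data to nominal visits, although for binary endpoints. The ambiguity remains.

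**The shortest lags may be unrealistic.** Appendix 5 does not say whether the 48 hours run from sampling or from the result, and samples go to a central laboratory. If results take 1-2 days (an assumption), lags become about 2-4 days. At 3-4 days the shares are 0%, 20% and 29%. This stands.

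**Stronger readings are not supported.**
- A reader might infer that every early visit lets the retest in. It does not: at lags of 3-5 days, 15 of the 27 early-visit combinations keep the scheduled value, including all of those at Week 2.
- A reader might infer that the shift is always toward normal. A confirmed abnormality stays abnormal, and with a platelet nadir at Week 4 a retest after Week 2 may be lower.
- A reader might infer that criteria based on two sequential values would be lost. That would follow only if the Section 6.6.2 summary were run on one record per window, and nothing says it is.

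**Few values are involved.** The dated retest rules apply only past set limits. In Phase 2, mean platelets at Week 4 and their 90% CI stayed within the normal range at both doses, and Section 4.3 reports one treated participant with a thrombocytopenia event and a count below half the lower limit of normal. This stands, and it is why the point is minor.

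**Conclusion.** Read literally, Appendix 2 allows a confirmatory retest to displace the scheduled abnormal laboratory value in by-visit tables. Both conditions are needed: the visit preceded the target day, and the retest lag was at most twice the days early. This is a stated rule with a selective effect, not merely an omission.

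Under the even-spread assumption, the share of retested values affected runs from 0% to 43%, depending on visit and lag. Movement of by-visit means and categories toward normal is expected but not certain. Its size cannot be computed, because the documents give neither the number of retests nor the distribution of visit days; the number of affected values is probably small. Any narrowing of the drug-placebo contrast is therefore a possibility, not a demonstrated result. Efficacy conclusions and participant-level counts of monitoring and discontinuation criteria are not shown to be affected. The conclusion also depends on CaPS not already excluding unscheduled records. Severity: minor.

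**What to change.** In SAP Appendix 2:
- Limit the closest-to-target and later-on-ties rule to efficacy variables.
- For by-visit laboratory, ECG and vital-sign tables, use the scheduled-visit value when the window contains one, and otherwise the first unscheduled value.
- State that retests and other unscheduled values go to the listings, to any worst-post-baseline summaries and to the Section 6.6.2 counts of monitoring and discontinuation criteria, and that these counts are run on all unwindowed data.
- Check the text against CaPS. If CaPS already does this, say so in the appendix and remove the conflicting wording.

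The cost is a few sentences in the SAP and a programming flag for scheduled records. No new data are needed, and no visit or retest requirement changes.
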